
	
10. Adequate baseline pulmonary function test (FEV1 > 2 L or $\geq 75\%$ of predicted for height and age).
 
11. Because the teratogenicity of pembrolizumab and IL-2 is not known,
 
 Female subject of childbearing potential (WOCP) must not be pregnant confirmed by a negative urine or serum pregnancy test within 72 hours of the study registration. If the urine test cannot be confirmed as negative, a serum pregnancy test will be required. 
12. < 2 lines of prior therapy for metastatic melanoma. Cannot have received prior therapy with HD IL-2. May have had one prior line of therapy that included a check point inhibitor.
 
13. Not received radiation therapy within 21 days of initiation of study treatment, and the measurable disease must have been outside of the radiation port.
 
14. More than 3 weeks must have elapsed since any prior systemic therapy at the time the subject receives the first dose of pembrolizumab. Subject's toxicities must have recovered to a grade 1 or less (except for toxicities such as alopecia or vitiligo)
 
15. No second active malignancy.
 
16. No autoimmune diseases (see full eligibility criteria)
 
17. Willingness and ability to comply with scheduled visits, treatment plans, laboratory tests, and other study procedures.
 
18. Provide written informed consent and HIPAA authorization for release of personal health information, approved by an Institutional Review Board/Independent Ethics Committee (IRB/IEC). HIPAA authorization may be included in the informed consent or obtained separately.

STATISTICAL CONSIDERATIONS	
The optimal two-stage design to test the null hypothesis that $P \leq 0.260$ versus the alternative that $P \geq 0.500$ with 80% power and 0.05 level of significance proceeds as follows. After testing the drug on 11 patients in the first stage, the trial will be terminated if 3 or fewer respond. If the trial goes on to the second stage, a total of 29 patients will be studied. If the total number responding is less than or equal to 11, the drug is rejected. The probability of early termination at stage 1 with a total sample size of 11 is 0.685; the probability of going on to stage 2 with a total sample size of 29 is 0.315. The sample size calculation is conducted using the software PASS 13 (NCSS, Kaysville, Utah 2014)

TOTAL NUMBER OF SUBJECTS	N = Up to 29 subjects

[figure not shown]
ESTIMATED ENROLLMENT PERIOD	Estimated 36 months

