5.2 HD IL-2 Administration

After completing the 2 cycles of pembrolizumab, High Dose Interleukin-2 (HD IL-2) will be administered. This will require a hospital stay of at least 5 days for each treatment cycle. Established guidelines will be followed for safely administering HD-IL-2 and managing toxicities from this treatment [31,32]. Two treatment cycles will be administered, Cycle 2 being separated from Cycle 1 by approximately 9 days after completion (assuming subject has recovered from Cycle 1 adequately to proceed with Cycle 2). Four weeks after completion of the 2 cycles (called a course of HD IL-2 therapy), disease status will be monitored via CT of the chest and abdomen/pelvis using revised RECIST guidelines (version v1.1, Section 9 of protocol).

Correlative research analyses in this phase include examining the relationship between changes in soluble PD-L1 level and Type 1 T helper cell/Type 2 T helper cell (Th1/Th2) ratios assessed after each of the two HD IL-2 cycles relative to baseline (i.e., pre-dose on Day 1 of Cycle 1 of pembrolizumab treatment), to the best clinical response (modified RECIST criteria) and to treatment outcome.

Drug	Dose	Route	Schedule	Cycle Length
IL-2	600,000 IU/kg ²	Intravenously (IV) over 15 minutes	Every 8 hours for up to 14 doses over 5 days	Days 1-5 = Cycle 1 9 days of rest in between Days 15-19 = Cycle 2

¹ A window of - 1 or + 2 days may be applied to all study visits to accommodate observed holidays, inclement weather, scheduling conflicts etc. Date and time of each drug administration should be clearly documented in subject's chart and electronic case report forms (eCRFs).

²Actual weight will be used unless the patient is 30% over ideal body weight in which case adjusted body weight will be used (Males: IBW = 50 kg + 2.3 kg for each inch over 5 feet.

Females: IBW = 45.5 kg + 2.3 kg for each inch over 5 feet); ABW = IBW + 0.4(actual weight - IBW)

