5.5 Use in Pregnancy

If a subject inadvertently becomes pregnant while on study treatment, the subject will immediately be removed from the study. The site will contact the subject at least monthly and document the subject's status until the pregnancy has been completed or terminated. The outcome of the pregnancy will be reported to Hoosier Cancer Research Network (HCRN) **within 1 business day** if the outcome is a serious adverse experience (e.g., death, abortion, congenital anomaly, or other disabling or life-threatening complication to the mother or newborn). HCRN will report this information **within 1 business day** to Prometheus. The study investigator will make every effort to obtain permission to follow the outcome of the pregnancy and report the

condition of the fetus or newborn to HCRN. If a male subject impregnates his female partner, he must immediately inform the site study personnel and the pregnancy reported and followed as described above.

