6.2 Dose Delays for HD IL-2

6.2.1 Start of New Cycle

A new treatment cycle will only be initiated when all of the following conditions are met:

- ANC $\geq 1,500 \times 10^9/L$
- Platelets $\geq 100 \times 10^9/L$
- Non-hematologic treatment related toxicities have improved to \leq Grade 1 or to the subject's baseline values (except alopecia)

If blood counts are below this threshold (first two bullet points), blood work is to be repeated weekly until counts are at an acceptable level. If treatment is unable to restart within 12 weeks of the planned treatment date, the subject will be permanently discontinued from study therapy.

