6.2 Protocol Therapy Discontinuation

In addition to discontinuation from therapy related to toxicities as outlined above, a subject will also be discontinued from protocol therapy and followed per protocol under the following circumstances outlined below. The reason for discontinuation of protocol therapy will be documented on the electronic case report form (eCRF)

- Documented disease progression
- Site investigator determines a change of therapy would be in the best interest of the subject
- Subject requests to discontinue protocol therapy, whether due to unacceptable toxicity or for other reasons
 - In a subject decides to prematurely discontinue protocol therapy (“refuses treatment”), the subject should be asked if he or she may still be contacted for further scheduled study assessments. The outcome of that discussion should be documented in both the medical records and in the eCRF.
- Female subject becomes pregnant
- HD IL-2 will be discontinued if there is a ≥ 12 -week delay between cycles
- Pembrolizumab will be discontinued if there is a ≥ 12 -week delay between cycles

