7. STUDY CALENDAR & EVALUATIONS

Study Evaluations Cycle = 21 days for Pembrolizumab Cycle = 5 days for HD IL-2	Screening	Cycles 1-2 Pembrolizumab (P)	End of Cycle 2 Pembro	Cycle 1 HD IL2	Cycle 2 HD IL2	Safety follow up visit ¹¹	Long-term Follow up ¹²
	-28 days	Day 1 (± 3 days)	Day 21 (± 3 days)	Days 1-5	Days 15-19	28 days post last dose (± 7 days)	Every 3 months (±14 days)
REQUIRED ASSESSMENTS							
Informed Consent/HIPPA authorization	X						
Medical History ¹	X						
Diagnosis and Staging ²							
Physical Exam	X	X	X	X	X	X	
Vital signs and ECOG Performance Status ³	X	X	X	X	X	X	
AEs & concomitant medications	X	X	X	X	X	X	
LABORATORY ASSESSMENTS							
Complete Blood Cell Count with diff (CBC)	X	X ¹⁰	X	X	X	X	
Comprehensive Metabolic Profile (CMP)	X	X ¹⁰	X	X	X	X	
PT/INR and aPTT	X	X ¹⁰					
Thyroid Function (TSH, T4, free T3)	X		X				
Vitamin D level	X						
Pregnancy test (serum or urine) (WOCBP) ⁴	X	X ⁴					
Urinalysis	X	X ¹⁰	X		X		
DISEASE ASSESSMENT							
Chest X-ray				X			
CT of chest ⁵	X		X			X	
CT or MRI of abdomen and pelvis ⁵	X		X			X	
CT or MRI Brain ⁵	X		X			X	
TREATMENT EXPOSURE							
Pembrolizumab		X					
HD IL-2				X	X		
SPECIMEN COLLECTION							
Archival Tumor Tissue ⁶	X						
Blood Samples ⁷		X ⁷	X	X	X ⁷		
Stool sample ⁸		X					

Study Evaluations Cycle = 21 days for Pembrolizumab Cycle = 5 days for HD IL-2	Screening	Cycles 1-2 Pembrolizumab (P)	End of Cycle 2 Pembro	Cycle 1 HD IL2	Cycle 2 HD IL2	Safety follow up visit ¹¹	Long-term Follow up ¹²
	-28 days	Day 1 (± 3 days)	Day 21 (± 3 days)	Days 1-5	Days 15-19	28 days post last dose (± 7 days)	Every 3 months (±14 days)
BANKING SAMPLES							
Whole blood, Plasma and PBMCs ⁹		X ⁹	X			X	
FOLLOW-UP							
Survival Status, Subsequent Therapy							X

Key to Footnotes

CBC with differential and platelet to include: Hgb, Hct, WBC, ANC, lymphocyte count, platelets. CMP to include sodium, potassium, chloride, creatinine, blood urea nitrogen; liver function tests (LFTs) to include AST, ALT, total bilirubin, alkaline phosphatase

1: Medical History to include documentation of prior anti-cancer treatment including medications (chemotherapy, checkpoint inhibitors, etc.), radiation, or surgery. A question of how the subject learned about the study will be asked.

2: Diagnosis and staging to include pathology report and Tumor Node Metastasis (TNM) staging.

3: Vital signs to include blood pressure, weight, and height (screening only) and ECOG performance status.

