4: For women of childbearing potential (WOCBP): urine or serum βhCG if clinically appropriate will be done during screening and within 72 hours of initiation of study treatment. If a urine test is done and it is positive or cannot be confirmed as negative, a serum pregnancy test will be required.

5: Appropriate scans including CT chest, abdomen/pelvis to assess disease status will be obtained within 4 weeks before initiation of study treatment (screening). Post treatment scans will be performed on Cycle 2 Day 21 (end of Cycle 2 pembrolizumab; +3 days) of pembrolizumab and Cycle 2 of HD IL-2; +9 days) of HD IL-2 including CT chest, abdomen/pelvis. CT or MRI of the brain should be done if clinically indicated at site investigator's discretion.

6: Required if available: submission of unstained slides from archived tumor tissue for PD-L1 expression are to be identified during screening and submitted after the patient is registered to the trial prior to Cycle 2 of pembrolizumab. If archived tumor tissue is not available, the patient does not need to undergo a biopsy to obtain tissue and is still eligible for study.

7: Required: submission of blood for serum (soluble PD-L1, Th1/Th2 ratio and arginine levels) will be collected pre-dose Cycle 1 Day 1 of pembrolizumab, and on Cycle 2 Day 21 (+3 days) of pembrolizumab. Blood samples for these levels will also be collected at the end of each of the HD IL-2 cycles; End of Cycle 1 sample will be drawn (+3 days) prior to dosing Cycle 1 Day 5 (after completion of HD IL-2). The end of Cycle 2 sample will be drawn (+ 9 days) at the end of Cycle 2 Day 19 (after completion of HD IL-2).

- 8: Required: submission of a stool specimen (for microbiome characterization) will be collected at baseline (pre-dose Cycle 1 Day1 of pembrolizumab). Stool for microbiome analysis will be performed prior to treatment. Subjects will be provided a kit with detailed instructions regarding collection of the sample prior to the timepoint it is due. Please see the CLM for additional details.
- 9: Optional: submission of whole blood, plasma and PBMCs for banking to be collected at baseline pre-dose Cycle 1 Day 1 of pembrolizumab and on Cycle 2 Day 21 (+3 days) of pembrolizumab. This sample will also be collected about 4 weeks after the last dose of HD IL-2 (safety visit)
- 10: For Cycle 1 Day of pembrolizumab only: labs do not need to be repeated if done within 7 days of Day 1.

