10.2.6 Side Effects

Please refer to the current version of the Investigator's Brochure for a complete list of adverse events.

The following adverse events (Grades 1-4) were seen in $\geq 30\%$ of 525 patients (255 with metastatic renal cell cancer and 270 with metastatic melanoma) treated with Proleukin®: hypotension (71%), diarrhea (67%), oliguria (63%), chills (52%), vomiting (50%), dyspnea (43%), rash (42%), bilirubinemia (40%), thrombocytopenia (37%), nausea (35%), confusion (34%), and creatinine increase (33%). Due to the potential severe adverse events that might accompany Proleukin therapy at the recommended dosages, thorough clinical evaluation will be performed to exclude subjects that are contraindicated to Proleukin therapy and patients that have significant cardiac, pulmonary, renal, hepatic, or CNS impairment. Adverse events are frequent, often serious, and sometimes fatal. Further details around frequency, reporting, and management of immune-related adverse events (irAEs) can be found in the current version of the Investigator's Brochure. In addition to the previously noted identified risks, infusion-related reactions are a risk but are not considered immune mediated; these are also further described in the current IB.

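### No pregnancy test is scheduled before either HD IL-2 cycle; the last one falls 42 to 45 days (or, on a favourable reading, about 21 days) before the earliest first IL-2 dose

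*Combined protocol and SAP*

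**What the plan says.** **Reason for testing.** Synopsis, key eligibility item 11, opens its pregnancy requirement with "Because the teratogenicity of pembrolizumab and IL-2 is not known". Both drugs are named.

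**When tests are scheduled.** In Section 7 the pregnancy-test row is marked at Screening and under Day 1 of pembrolizumab Cycles 1-2. The cells for End of Cycle 2 pembrolizumab, HD IL-2 Cycle 1 and HD IL-2 Cycle 2 are blank. Footnote 4 states that the test "will be done during screening and within 72 hours of initiation of study treatment". Section 12.1 identifies pembrolizumab as the first treatment. Section 3.1 item 14 separately requires a negative serum test within 3 days before registration, which also precedes pembrolizumab.

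**What must be true before HD IL-2.** Section 5.2: "After completing the 2 cycles of pembrolizumab, High Dose Interleukin-2 (HD IL-2) will be administered". Section 6.2.1: "A new treatment cycle will only be initiated when all of the following conditions are met", followed by ANC, platelets and recovery of non-hematologic toxicity. Section 10.2.6 adds that "thorough clinical evaluation will be performed to exclude subjects that are contraindicated to Proleukin therapy", without naming a pregnancy test.

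**What happens if pregnancy is found.** Section 5.5: "If a subject inadvertently becomes pregnant while on study treatment, the subject will immediately be removed from the study". The Protocol Therapy Discontinuation section lists "Female subject becomes pregnant" among its reasons to stop.

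**The concern.** The regimen is sequential, with two drugs started about six weeks apart. The protocol gives the same fetal-risk reason for both, but the test close to dosing is tied only to the first drug. The rules on removal and discontinuation take effect only once a pregnancy is known. Nothing scheduled between the start of pembrolizumab (or, at best, its second dose) and the start of HD IL-2 would reveal an early one. A woman who conceived in that interval could receive up to 28 HD IL-2 doses (2 cycles × up to 14) before any test prompted by the protocol. Other checks, such as physical examination, CBC and CMP, are repeated at both HD IL-2 cycles, so the omission stands out in the calendar itself.

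**Working it through.** The documents state no interval from pregnancy test to IL-2, so there is no figure of theirs to reproduce. The gap follows from the schedule.

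**Inputs**
- Pembrolizumab: two 21-day cycles (Section 5.1).
- HD IL-2 follows pembrolizumab with no fixed gap (Sections 5.1 and 5.2), so only the earliest start can be dated.
- HD IL-2 Cycle 1 is Days 1-5 and Cycle 2 is Days 15-19, so Cycle 2 starts 14 days after Cycle 1 (Section 5.2).
- Footnote 4's test is taken on the day of, or up to 72 hours (3 days) before, the first pembrolizumab dose.
- A delay of up to 12 weeks is tolerated (Section 6.2.1).

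**Day count**, with first pembrolizumab = Day 1
- Pembrolizumab Cycle 2 Day 1 = 1 + 21 = Day 22.
- Last day of pembrolizumab Cycle 2 = Day 42.
- Earliest HD IL-2 Cycle 1 Day 1 = Day 43.
- Earliest HD IL-2 Cycle 2 Day 1 = 43 + 14 = Day 57.

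**Gap = day of IL-2 dose − day of last scheduled test**

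| Reading of the schedule | To first IL-2 dose | To IL-2 Cycle 2 |
|---|---|---|
| Footnote 4 literally: test only around first pembrolizumab | 43 − 1 = 42; 42 + 3 = 45 days | 57 − 1 = 56; 56 + 3 = 59 days |
| Calendar column means Day 1 of both pembrolizumab cycles | 43 − 22 = 21 days | 57 − 22 = 35 days |

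The two rows are alternative readings, not the ends of one range. Footnote 4 is the more specific text, so 42 to 45 days is the better-supported figure and about 21 days is the most favourable. Visit windows move these by a few days.

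**Delay.** Each day of delay before IL-2 adds a day. A delay approaching the 12-week limit (84 days) would take the first-dose gap towards 42 + 84 = 126 to 45 + 84 = 129 days, or 21 + 84 = 105 days on the favourable reading. Section 6.2.1 asks for repeat blood counts during a delay caused by low counts, but no repeat pregnancy test.

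**With a test within 72 hours before each HD IL-2 cycle**, the gap is 0 to 3 days at both cycles, whatever the delay.

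**The case against.** The protocol does not ignore the risk. Women of childbearing potential must use two contraceptive methods or abstain, from consent to 120 days after treatment. Section 5.4 bars anyone whose compliance with contraception is in question. Physical examination and adverse-event review are scheduled at the end of pembrolizumab Cycle 2 and at both IL-2 cycles. The calendar, footnote 4 and Section 6.2.1 agree with one another about IL-2, and none of them promises a test there. All of this stands, and it makes an undetected pregnancy less likely. But contraception does not detect pregnancy, examination may miss an early one, and the protocol itself requires tests alongside contraception at entry.

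Some stronger readings are tempting but not supported:

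- **That no test would be done in practice.** Section 5.2 invokes established guidelines for giving HD IL-2 safely, Section 5.2.1 refers toxicity management to the Study Procedures Manual, and Section 10.2.6 commits to a clinical evaluation. The guidelines and the manual are not in the documents. What can be said is that the protocol text names no test.
- **That footnote 4's proviso about clinical appropriateness makes the test near first dose optional, so the gap is longer still.** The next sentence deals with what follows if urine is used, so the proviso more naturally governs the choice between urine and serum. Item 14 mandates the serum test before registration in any case.
- **That the definition of postmenopausal should be aligned to Section 5.4 as the stricter one.** Section 5.4 adds an age floor of 45 but does not require that menopause be natural, as item 14 does. It is therefore not uniformly stricter, and the matter is separate from IL-2 timing.

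**Conclusion.** The point holds as a gap in the safety schedule. As written, the protocol requires no pregnancy test at or shortly before either HD IL-2 cycle, although it gives unknown teratogenicity of IL-2 as a reason for testing. At the earliest possible start, the last scheduled test is six weeks old on the literal text and three weeks old on the favourable one. By IL-2 Cycle 2 it is two weeks older.

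These figures assume that HD IL-2 begins the day after pembrolizumab Cycle 2 ends, so later starts make them larger. They also assume that footnote 4's test is done as scheduled. The number of women of childbearing potential and the chance of pregnancy under the contraception rule are not given, so the expected number of exposures cannot be estimated; with at most 29 subjects it would be small. The consequence is confined to participant safety. Sample size, error rates and the response-rate analysis do not change. This is a worthwhile, low-cost improvement and not a defect that threatens the trial.

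**What to change.** Three matching edits:

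1. In footnote 4 of Section 7, after the existing timing, add: *and within 72 hours before Day 1 of each HD IL-2 cycle*. Keep the rule that a serum test follows a urine test that is positive or cannot be confirmed negative.
2. In the pregnancy-test row of the calendar, mark the HD IL-2 Cycle 1 and HD IL-2 Cycle 2 cells.
3. In Section 6.2.1, add the condition: *negative urine or serum βhCG within 72 hours (women of childbearing potential)*.

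If the Study Procedures Manual or the IL-2 guidelines already call for a test, the same edits bring the protocol into line with them.

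The cost is amendment wording and up to two added βhCG tests per woman of childbearing potential. The ceiling is 2 × 29 = 58 tests if every subject were such a woman, which overstates the likely number. CBC and CMP are already drawn at both HD IL-2 cycles, so no new visit or procedure is needed.

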2.1.3 Correlative/Exploratory Objectives

- Correlate PD-L1 expression in archived diagnostic tumor tissue with best clinical response (revised RECIST 1.1 criteria) and treatment outcome in subjects with stage IV malignant melanoma.
- Correlate Th1/Th2 ratio and myeloid-derived suppressor cells (MDSCs) in peripheral blood during therapy with best clinical response (revised RECIST criteria) and treatment outcome in subjects with stage IV malignant melanoma. Data will be collected prior to treatment, during treatment after the 2nd dose of pembrolizumab and after each cycle of HD IL-2.
- Correlate the change in soluble PD-L1 and arginine level in plasma during therapy with best clinical response (revised RECIST1.1 criteria) and treatment outcome in subjects with stage IV malignant melanoma. Data will be collected prior to treatment, during treatment after the 2nd dose of pembrolizumab and after each cycle of HD IL-2.
- Correlate intestinal microbiome at baseline with best clinical response (revised RECIST 1.1 criteria) and treatment outcome in subjects with stage IV malignant melanoma.

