8. BIOSPECIMEN STUDIES AND PROCEDURES

8.1 Correlate PD-L1 expression in archived diagnostic tumor tissue with best clinical response (revised RECIST criteria) and treatment outcome in subjects with stage IV malignant melanoma

Expression of PD-L1 in archived diagnostic tumor tissue will be determined by IHC by referring laboratory using anti-PD-L1 antibody clone 22C3, and will be correlated with clinical response assessed by imaging. Unstained slides are to be submitted; a tumor block is not acceptable.

8.2 Correlate the change in soluble PD-L1 and arginine levels in plasma during therapy with best clinical response (revised RECIST criteria) and treatment outcome in subjects with stage IV malignant melanoma

Whole blood for serum submission will be collected pre-dose Cycle 1 Day 1 of pembrolizumab, and on Cycle 2 Day 21 (+3 days) of pembrolizumab. Blood samples for these levels will also be collected at the end of each of the HD IL-2 cycles; End of Cycle 1 sample will be drawn prior to dosing Cycle 1 Day 5 (+3 days). The end of Cycle 2 sample will be drawn (+ 9 days) at the end of Cycle 2 Day 19 for analysis of soluble PD-L1 and arginine levels. Change in soluble PD-L1 and arginine levels as a result of treatment will be examined in relation to the best clinical response (RECIST, v1.1) and treatment outcome.

8.3 Correlate Th1/Th2 ratio and MDSCs in peripheral blood during therapy with best clinical response (revised RECIST criteria) and treatment outcome in subjects with stage IV malignant melanoma

Whole blood for serum submission will be collected pre-dose Cycle 1 Day 1 of pembrolizumab, and on Cycle 2 Day 21 (+3 days) of pembrolizumab. Blood samples for these levels will also be collected at the end of each of the HD IL-2 cycles; End of Cycle 1 sample will be drawn prior to dosing Cycle 1 Day 5 (+3 days). The end of Cycle 2 sample will be drawn (+ 9 days) at the end of Cycle 2 Day 19 for analysis of Th1/Th2 ratio levels and MDSC quantification. Change in Th1/Th2 ratio and MDSCs levels as a result of treatment will be examined in relation to the best clinical response (RECIST, v1.1) and treatment outcome.

8.4 Correlate intestinal microbiome at baseline with best clinical response (revised RECIST criteria) and treatment outcome in subjects with stage IV malignant melanoma

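### The IL-2 Cycle 1 research blood sample is timed both before Day 5 dosing and after IL-2 completion, and the MDSC specimen is not properly specified

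*Combined protocol and SAP*

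**What the plan says.** **Timing.** The correlative objectives in Section 2.1.3 ask for blood data "during treatment after the 2nd dose of pembrolizumab and after each cycle of HD IL-2". Section 12.2.3 carries that schedule into the analysis, which relates change from the pre-pembrolizumab baseline to best response and treatment outcome.

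The draw times appear in three places. Footnote 7 of Section 7 says: "End of Cycle 1 sample will be drawn (+3 days) prior to dosing Cycle 1 Day 5 (after completion of HD IL-2". Sections 8.2 and 8.3 each say: "End of Cycle 1 sample will be drawn prior to dosing Cycle 1 Day 5 (+3 days". All three introduce these as end-of-cycle samples. For the second IL-2 cycle footnote 7 says: "The end of Cycle 2 sample will be drawn (+ 9 days) at the end of Cycle 2 Day 19 (after completion of HD IL-2". Section 5.2 gives the IL-2 schedule: "Every 8 hours for up to 14 doses over 5 days".

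**Specimens.** One objective in Section 2.1.3 reads: "Correlate Th1/Th2 ratio and myeloid-derived suppressor cells (MDSCs) in peripheral blood during therapy with best clinical response". Section 8.3 uses its samples "for analysis of Th1/Th2 ratio levels and MDSC quantification", but the collection it describes is whole blood to be submitted as serum. Footnote 7 lists the required collection as "submission of blood for serum (soluble PD-L1, Th1/Th2 ratio and arginine levels", without MDSCs. Section 12.2.3 does not mention MDSCs either. Soluble PD-L1 and arginine are plasma measures in Section 2.1.3 and in the heading of Section 8.2. They are serum measures in footnote 7 and in the text of Section 8.2, and either one in the synopsis.

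**The concern.** A site that follows Sections 8.2 and 8.3 literally would sample a fully dosed patient during IL-2 treatment. A site that follows the parenthesis in footnote 7 would sample after it. Both would be compliant, and the values would be analysed together as the level after Cycle 1. A subject who stops IL-2 before Day 5 is sampled after the last dose under either text. Under the pre-dose reading, sampling time would therefore also be linked to how much IL-2 the subject received.

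The MDSC gap is of a different kind. MDSCs are cells and the only collection described for them is for serum, so a site has no instruction to keep anything that could be counted. The trial enrols up to 29 subjects, or 11 if it stops after the first stage, and a mistimed or wrongly processed sample cannot be taken again.

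**Working it through.** The plan gives no figure for this point, so the check is a dose count and a comparison of sections.

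**1. Doses still to come at a pre-dose Day 5 draw.** Inputs from Section 5.2: 14 doses, one every 8 hours, starting on Day 1. Assumptions: no dose is skipped, the draw precedes the first Day 5 dose, and the first dose is given at clock hour s of Day 1, which the documents do not fix.

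Dose k is given at hour s + 8(k − 1), counted from the start of Day 1. Day 5 begins at hour 96.

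| First dose at hour | Doses before Day 5 | First dose on Day 5 | Dose 14 | Doses still to come |
|---|---|---|---|---|
| s = 0 | 12 | dose 13, hour 0 + 96 = 96 | hour 0 + 104 = 104, Day 5 | 14 − 12 = 2 |
| s = 8 | 11 | dose 12, hour 8 + 88 = 96 | hour 8 + 104 = 112, Day 5 | 14 − 11 = 3 |
| s = 16 | 10 | dose 11, hour 16 + 80 = 96 | hour 16 + 104 = 120, Day 6 | 14 − 10 = 4 |

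A start at hour 23 also leaves 4. In the last row dose 14 falls on Day 6. If dosing is held to calendar Days 1–5, at most 13 doses fit and 3 remain.

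**2. Spread allowed by the window.** Take s = 0 and count +3 days as 72 hours from the pre-dose Day 5 point. The draw may then fall anywhere from hour 96 to hour 96 + 72 = 168. Against dose 14 at hour 104, that is from 104 − 96 = 8 hours before the last planned dose to 168 − 104 = 64 hours after it. A window running past the remaining doses does not fit a pre-dose draw.

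**3. When the two times agree.** They are compatible only if IL-2 has stopped before Day 5, which a schedule of up to 14 doses allows.

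**4. Time points affected.** There are four research blood times: baseline, pembrolizumab Cycle 2 Day 21, end of IL-2 Cycle 1 and end of IL-2 Cycle 2. Only the third is contradictory.

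**5. Could another collection supply the MDSC count?** The only PBMC collection (footnote 9 and Section 8.5) is optional and for banking. It is taken at baseline, pembrolizumab Cycle 2 Day 21 and the safety visit, with no draw at the end of either IL-2 cycle.

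**6. Effect on the main design.** None of these inputs enters the two-stage calculation. That calculation reproduces: the sum over x = 0 to 3 of C(11, x) × 0.26^x × 0.74^(11 − x) is 0.6854, against 0.685 stated in Section 12.3.

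**The case against.** The intended time can largely be recovered. All three sections call these end-of-cycle samples, the objective says after each cycle, footnote 7 adds completion of IL-2, and a +3 day window suits only a draw after dosing. The pre-dose words look like a drafting slip. That is probably right, but Sections 8.2 and 8.3 give only the pre-dose time, so a site working from them has no reason to read past it. That sites will diverge is a risk, not a certainty.

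A reader might infer that every subject's two IL-2 samples are compromised. The documents do not support that. The Cycle 2 time is clear, a subject who stops before Day 5 satisfies both Cycle 1 conditions, and a subject taken off therapy before IL-2 has no IL-2 samples. Nor do the differing windows (+3 and +9 days) amount to an error. The planned analysis compares each time with baseline, not Cycle 1 with Cycle 2, so matched windows would be a preference.

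On MDSCs, a reader might infer that the count is impossible because serum holds no cells. Whole blood is what is drawn, and a cell fraction could be kept. Footnote 8 cites a further manual (CLM) for the stool sample. It is not among the documents, and it may cover blood handling. What stands is narrower: the protocol does not specify a suitable specimen, and a manual would not remove contradictory protocol text.

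**Conclusion.** The point holds as an inconsistency to be reconciled. One of four research blood times is contradictory. For a patient still being dosed on Day 5, a pre-dose draw comes before the last 2 to 4 of up to 14 planned doses. That range assumes uninterrupted 8-hourly dosing and depends on the Day 1 start hour; the figure of 4 counts a dose that falls on Day 6. How far marker values would shift cannot be sized, because the documents give no within-cycle marker data.

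The MDSC specimen is unspecified and MDSCs are absent from both the required-sample footnote and the analysis section. The matrix for soluble PD-L1 and arginine is inconsistent.

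It would go too far to conclude that the exploratory objectives cannot be met. Archival-tissue PD-L1 and the baseline microbiome do not use these samples, and the other three blood times are clear. The primary endpoint, sample size and error rates are untouched, so this is a minor correction worth making.

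**What to change.** - In footnote 7 and Sections 8.2 and 8.3, delete the words that place the Cycle 1 sample before Day 5 dosing. State that it is drawn after the last IL-2 dose actually given in that cycle, +3 days.
- Record the date and time of the sample. Section 5.2 already requires the date and time of each dose, so time since last dose can be derived.
- Add MDSCs to footnote 7 and Section 12.2.3, and name a cell-containing specimen for them at the existing draws in footnote 7 and Section 8.3.
- Name one matrix for soluble PD-L1 and arginine, and use it in the synopsis, Section 2.1.3, footnote 7, and the heading and text of Section 8.2.

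The Cycle 2 time and window can stay as they are. The cost is wording in these sections and possibly one extra tube, with its handling, at draws that already take place. No visit or treatment changes.
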